### **Intensity and Causality Assessments**

Where appropriate, the Investigator must assess the intensity (severity) of the AE based on medical judgment with consideration of any subjective symptom(s), as defined below:

### ***Intensity (Severity)***

Mild        An AE is mild if the subject is aware of but can easily tolerate the sign or symptom.

Moderate    An AE is moderate if the sign or symptom results in discomfort significant enough to cause interference with the subject's usual activities.

Severe      An AE is severe if the sign or symptom is incapacitating and results in the subject's inability to work or engage in their usual activities.

For every AE in the study, the Investigator must assess the causality (Related or Not Related to the medical device or study procedure). An assessment of causality will also be performed by Study Sponsor utilizing the same definitions, as shown below:

[figure not shown]
### ***Causality***

Related      An AE classified as related may be either definitely related or possibly related where a direct cause and effect relationship with the medical device or study procedure has not been demonstrated, but there is a reasonable possibility that the AE was caused by the medical device or study procedure.

Not Related    An AE classified as not related may either be definitely unrelated or simply unlikely to be related (ie, there are other more likely causes for the AE).

The Study Sponsor will assess the AEs and may upgrade the Investigator's assessment of seriousness and/or causality. The Study Sponsor will notify the Investigator of any AEs that is upgraded from non-serious to serious or from unrelated to related.

Furthermore, the Study Sponsor shall promptly conduct an evaluation of any unanticipated adverse device effect, including anticipated adverse events that occur in unanticipated severity or frequency. The results of this evaluation will be reported to the FDA, the IRB, and participating Investigators within 10 working days upon receiving notification of the effect.

## 11.5 Unmasking of the Study Treatment

Not applicable; this study is open-label.

## 11.6 Follow-Up of Subjects with Adverse Events

The Investigator is responsible for adequate and safe medical care of subjects during the study and for ensuring that appropriate medical care and relevant follow-up procedures are maintained after the study.

The Investigator should provide the Study Sponsor with any new safety information (which includes new AEs and changes to previously reported AEs) that may affect the safety evaluation of the device. For AEs that are unresolved/ ongoing at time of subject exit from study, any additional information received at follow-up should be documented in the eCRFs up to study completion (ie, database lock).

Any additional data received up to 6 months after subject discontinuation or exit must be documented and available upon the Study Sponsor's request. All complaints received after this time period will be considered and processed as spontaneous (following the postmarket vigilance procedures) and should be communicated to the medical device's manufacturer as per local requirements.

The Investigator should also report complaints on non-Alcon products directly to the manufacturer as per the manufacturer's instructions or local regulatory requirements.

## 11.7 Pregnancy in the Clinical Study

Pregnancy is not reportable as an AE; however, complications may be reportable and will be decided on a case-by-case basis. An Alcon form will be utilized to capture all pregnancy-related information until birth of the child.

# 12 ANALYSIS PLAN

This information will also be contained within a separate biostatistical analysis plan which will be prepared and finalized prior to database lock.

Counts and percentages will be presented as categorical variables. N, mean, standard deviation, median, minimum, and maximum will be presented for continuous variables.

## 12.1 Subject Evaluability

Final subject evaluability must be determined prior to locking the database, based upon the Deviations and Evaluability Plan.

## 12.2 Analysis Sets

All eligible subjects will be screened to determine if they meet all inclusion and no exclusion criteria. Subjects who provide informed consent will be considered enrolled in the study.

[figure not shown]
Refractive surgery will be bilaterally performed for all subjects. Both eyes from each subject will be used for analysis.

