Key exclusion criteria  (See Section 8.2 for a complete list of exclusion criteria)	
Subjects must not meet exclusion criteria as listed in Section 8.2.
 
Key Exclusion Criteria include:
 

• History or evidence of active or inactive corneal disease or retinal vascular disease, keratoconus, glaucoma (or suspect), or cataract

• Previous intraocular or corneal surgery

• Intent to have monovision treatment

• Increased risk for developing strabismus post-treatment

Data analysis and sample size justification	
The safety analysis set (SAF) will include all eyes for which refractive surgery is attempted with test device (regardless of success or failure). Full Analysis Set (FAS) will include all eyes with successful refractive surgery having at least 1 postoperative visits. The primary analysis set for effectiveness analysis will be the FAS.
 
[REDACTED]
 
[REDACTED]
 
[REDACTED]

Subject evaluability will be determined prior to locking database. No interim analysis is planned.

In order to evaluate efficacy of the WaveLight EX500 excimer laser system for the correction of hyperopia with and without astigmatism, the following primary effectiveness analyses will be conducted.

Test 1: Percentage of eyes with MRSE within  $\pm 0.50$  D at refractive stability is greater than the target level of 50%

Test 2: Percentage of eyes with MRSE within  $\pm 1.00$  D at refractive stability is greater than the target level of 75%.

For the statistical test of primary effectiveness variables, the exact test of a binomial proportion will be used, and the p-values will be provided for Test 1 and Test 2.

Type 1 error at each test is set as one-sided 2.5%.

Refractive surgery will be bilaterally performed for all subjects. Both eyes from each subject will be used for analysis.

	
Each safety variable will be summarized descriptively. Incidence of adverse events will be calculated.

Key words	

• LASIK

• Hyperopia

• Astigmatism

Associated materials	

• WaveLight EX500 Laser System

• WaveCard

**Table 3–1** Schedule of Study Procedures and Assessments

[figure not shown]
	Screening 	Surgery	Postoperative							Other	

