	Visit 0	Visit 00/ Visit 00A 	Visit 1/ Visit 1A	Visit 2/ Visit 2A	Visit 3/ Visit 3A	Visit 4/ Visit 4A	Visit 5/ Visit 5A	Visit 6/ Visit 6A	Visit 7/ Visit 7A	Early Exit	USV 
Procedure/ Assessment	Day -45 to -1	Day 0	Day 1	Day 5 to 9	Day 21 to 35	Day 70 to 98	Day 147 to 182	Day 245 to 301	Day 330 to 420		
Informed Consent	X										
Inclusion/Exclusion	X	X 									
Demographics	X										
Medical History 	X										
Concomitant Medications 	X	X	X	X	X	X	X	X	X	X	X
Urine Pregnancy Test 	X										
Cycloplegic Refraction	X						X		X	X	
Mesopic Pupil Size	X										
Aberrometry	X										
Keratometry	X										
<hr/>											
Topography 	X										
UCDVA	X		X	X	X	X	X	X	X	X	X
Manifest/Subjective Refraction	X 			X	X	X	X	X	X	X	
BCDVA	X			X	X	X	X	X	X	X	
IOP	X				X	X	X	X	X	X	X
Slit Lamp Examination	X		X	X	X	X	X	X	X	X	X
Dilated Fundus Examination	X						X		X	X	X
LASIK surgery		X									
<hr/>											
Adverse Events 	X	X	X	X	X	X	X	X	X	X	X
Device Deficiencies	X	X	X	X	X	X	X	X	X	X	X

[figure not shown]
1. Screening should cover evaluation of both eyes with intent for bilateral treatment on the same surgery day.
2. 'A" denotes visit for 2nd eye treated. Although visits are listed for 1st and 2nd eye treatment, the expectation is to perform surgery and follow-up visits on the same day for both eyes.
3. Unscheduled visit – additional clinical assessments may be performed per the Investigator's discretion.
4. Confirm inclusion/exclusion criteria as needed.
5. Refer to Protocol Section 10.2.13, electronic case report form (eCRF) Guidelines, and Manual of Procedures (MOP) for collection and documentation requirements.
6. Refer to Protocol Sections 9.6 and 10.2.4, eCRF Guidelines, and MOP for collection and documentation requirements.
7. Required only for women of child-bearing age, not postmenopausal or surgically sterile women. Data is collected in source only.
8. Allow Investigator to use best judgement for post-op care.
9. Subjective Refraction to assess for inclusion stability at Screening (Visit 0) should be performed on the site's chart; subjective refraction for VA testing will be refraction on Sponsor provided electronic chart.  
[REDACTED] [REDACTED]
11. Refer to Protocol Sections 10.2.2 and 11, eCRF Guidelines, and MOP for collection and documentation requirements.

[figure not shown]

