#### 12.5.1.1 Statistical Hypotheses

The statistical test for primary variables will be performed using the exact test of a binomial proportion. The null and alternative hypotheses are:

Test 1:

$$H_0: \pi_1(\text{EX500}) = 50.0\%$$

$$H_1: \pi_1(\text{EX500}) > 50.0\%$$

Test 2:

$$H_0: \pi_2(\text{EX500}) = 75.0\%$$

$$H_1: \pi_2(\text{EX500}) > 75.0\%$$

where  $\pi_1(\text{EX500})$  is the population proportion of eyes in the EX500 group with MRSE within  $\pm 0.50$  D at refractive stability, and  $\pi_2(\text{EX500})$  is the population proportion of eyes in the EX500 group with MRSE within  $\pm 1.00$  D at refractive stability. The constants 50.0% in Test 1 and 75.0% in Test 2 are the target levels for these MRSE parameters referred to from the FDA Checklist of Information Usually Submitted in an IDE (1996).

The p-values will be provided for Test 1 and Test 2. [REDACTED]

[REDACTED]

[REDACTED]

[figure not shown]
[REDACTED]

[REDACTED]

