#### 12.5.1.2 Analysis Methods

The FAS will be used for this analysis. The number and percentage of eyes meeting each of the primary effectiveness endpoints will be calculated. The effectiveness criteria will be considered to have been met if the percentage meets or exceeds the target rate at the time of

refractive stability for all primary effectiveness endpoints. These analyses will be performed for the whole FAS as well as stratified by preoperative MRSE subgroups. An analysis will be performed once refractive stability is achieved; a final summary of these endpoints will be performed once the one-year follow-up is complete.

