2.1.2.1 Refractive Stability

Stability analyses will be performed on eyes that have every follow-up exam from 1 month up to the stability time point [REDACTED] as well as on the eyes that have 2 consecutive exams, but not necessarily every follow-up exam. The following stability analyses will be performed for the time intervals between all consecutive pairs of scheduled postoperative refractions:

- Percentage of eyes that achieve:
 - a change of ≤ 1.00 D of MRSE between two refractions performed at 1 month and 3 months, and between subsequent refractions performed at least 3 months apart;
 - a change of ≤ 0.50 D of MRSE between two refractions performed at 1 month and 3 months, and between subsequent refractions performed at least 3 months apart;
- Mean overall change and change per month in MRSE between consecutive scheduled visits as determined by a paired analysis;
- Mean \pm SD MRSE for the preoperative and each postoperative visit;
- Assessment of cylinder stability for correction of spherocylindrical refractive errors

Refractive stability is achieved at the latter of two postoperative manifest refractions performed at least 3 months apart or at 3 months after surgery when compared with the 1-month interval, when all of the following recommended criteria are met:

- At least 95% of the treated eyes have a change ≤ 1.00 D of MRSE between the 2 refractions;
- The mean rate of change in MRSE, as determined by a paired analysis, is ≤ 0.5 D per year (0.04 D/month) over the same time period;
- The mean rate of change of MRSE decreases monotonically over time, with a projected asymptote of zero or a rate of change attributable to normal aging;

- The 95% confidence interval for the mean rate of change in MRSE includes zero or a rate of change attributable to normal aging; and
- Stability is confirmed at least 3 months after the stability time point by a statistically adequate subgroup [REDACTED]

The primary effectiveness endpoints for the study can only be evaluated once refractive stability has been established [REDACTED] as well as on the eyes that had 2 consecutive exams, but not necessarily every follow-up exam.

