4.3 Statistical Methods for Efficacy Analyses

The FAS will be used for this analysis. The number and percentage of eyes meeting each of the primary effectiveness endpoints will be calculated. The effectiveness criteria will be considered to have been met if the percentage meets or exceeds the target rate at the time of refractive stability for all primary effectiveness endpoints. [REDACTED]

[REDACTED]

[REDACTED]

[figure not shown]

Table 4-1 summarizes the key efficacy analyses.

Table 4-1 Summary of Analysis Strategy for Key Efficacy Endpoints

Endpoint	Statistical Method	Analysis Set	Missing Data Approach
Primary			
Percentage of eyes with MRSE within ± 0.50 D at refractive stability (Target: > 50%)	Exact test of a binomial proportion	FAS	Observed data only
Percentage of eyes with MRSE within ± 1.00 D at refractive stability (Target: > 75%)	Exact test of a binomial proportion	FAS	Observed data only

The subject data listings of each effectiveness variable will be provided.

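### Both eyes of each subject enter an exact binomial test that assumes independent eyes, so the stated one-sided 2.5% per test is not assured

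*Protocol*

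**What the plan says.** Every subject is to have bilateral surgery, and "Both eyes from each subject will be used for analysis" (Protocol 12.2; the Protocol Summary and SAP 1.2 say the same). The full analysis set is a set of eyes, not of subjects (Protocol 12.2.2, SAP 2.1.1). The two eyes share their timing: footnote 2 to Protocol Table 3-1 says that "the expectation is to perform surgery and follow-up visits on the same day for both eyes".

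On the method, Protocol 12.5.1.1 says "The statistical test for primary variables will be performed using the exact test of a binomial proportion", and SAP 4.2 repeats it. SAP Table 4-1 gives "Exact test of a binomial proportion" for both endpoints, on observed data in the full analysis set. The Protocol Summary fixes the level: "Type 1 error at each test is set as one-sided 2.5" (per cent). The null values are 50% and 75%: "The constants 50.0% in Test 1 and 75.0% in Test 2 are the target levels for these MRSE parameters".

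The readable text of either document contains no within-subject correlation, cluster adjustment, design effect or one-eye analysis. Text after the sentence that promises the p-values is redacted in Protocol 12.5.1.1 and SAP 4.2.

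**The concern.** An exact binomial test is exact only if the observations are independent. Two eyes of one person, treated by the same method and normally in the same session, are likely to have positively correlated refractive outcomes. The percentage then varies more from trial to trial than the binomial distribution allows, and a result at the binomial cut-off is less unusual under the null than its p-value says.

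The p-values for Test 1 and Test 2 are at stake. They are judged against a stated 2.5% and will support an application for registration in Japan.

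**Working it through.** **Inputs.** Planned completers are about 50 eyes in 25 subjects, and planned treated are about 60 eyes in 30 subjects (Protocol Summary). With the 10% loss to follow-up in Protocol 8, 30 x 0.9 = 27 subjects, or 54 eyes. The nulls are 0.50 and 0.75, at one-sided 0.025 per test. The correlation rho is not in the documents, so the range used here is an assumption.

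**Step 1: the plan's own level.** With independent eyes, the cut-off is the smallest r with P(X >= r | n, p0) <= 0.025.

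| Eyes | Test 1 cut-off (size) | Test 2 cut-off (size) |
|---|---|---|
| 50 | 33 (1.64%) | 44 (1.94%) |
| 54 | 35 (2.01%) | 47 (2.41%) |
| 60 | 39 (1.37%) | 52 (2.12%) |

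All are at or below 2.5%, so the stated level holds under independence. The shortfall below 2.5% comes from discreteness and leaves some slack.

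**Step 2: paired eyes.** With success probability p and q = 1 - p, each subject has

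- P(both) = p² + rho·p·q
- P(one) = 2pq(1 - rho)
- P(neither) = q² + rho·p·q

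The variance of the percentage over n eyes is pq(1 + rho)/n, which is 1 + rho times the binomial value. At rho 0.5 the three probabilities are 0.375, 0.25 and 0.375 for Test 1, and 0.65625, 0.1875 and 0.15625 for Test 2. Convolving them over 25, 27 or 30 subjects gives the exact distribution of the total. The upper tail at the Step 1 cut-offs is the true size.

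| rho | 50 eyes, T1/T2 | 54 eyes, T1/T2 | 60 eyes, T1/T2 |
|---|---|---|---|
| 0 | 1.6% / 1.9% | 2.0% / 2.4% | 1.4% / 2.1% |
| 0.1 | 2.1% / 2.4% | 2.5% / 3.0% | 1.8% / 2.6% |
| 0.3 | 3.1% / 3.5% | 3.6% / 4.2% | 2.7% / 3.8% |
| 0.5 | 4.1% / 4.7% | 4.8% / 5.5% | 3.6% / 5.0% |
| 0.8 | 5.7% / 6.6% | 6.4% / 7.4% | 5.1% / 6.9% |

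Size passes 2.5% at rho of about 0.18/0.11 (50 eyes), 0.09/0.02 (54) and 0.26/0.07 (60). At 50 eyes it reaches 5% at rho of about 0.67/0.55.

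**Step 3: effect on a p-value.** Use an effective sample size n_eff = n/(1 + rho), with x_eff = (x/n)·n_eff, and take p from the beta form I_p0(x_eff, n_eff - x_eff + 1). For 33/50 at rho 0.5, n_eff = 50/1.5 = 33.3, x_eff = 0.66 x 33.3 = 22.0 and p = 0.046.

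| Result | rho 0 | rho 0.3 | rho 0.5 | rho 0.8 |
|---|---|---|---|---|
| 33/50, Test 1 | 0.016 | 0.033 | 0.046 | 0.067 |
| 44/50, Test 2 | 0.019 | 0.040 | 0.055 | 0.080 |

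These run a little above the exact paired tails, which at rho 0.5 are 0.041 and 0.047 (Step 2). The direction is the same.

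**Step 4: does a clustered test hold the level?** The test set out under the fix estimates rho from the data. It was enumerated over all outcomes for rho from 0 to 0.9 at both nulls. Its size is 1.2% to 2.2% with 25 subjects, 1.5% to 2.3% with 27 and 1.3% to 2.0% with 30.

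**The case against.** The strongest objection is that no visible conclusion of the trial turns on these p-values. Protocol 12.5.1.2 says "The effectiveness criteria will be considered to have been met if the percentage meets or exceeds the target rate", SAP 4.3 says the same, and pairing does not bias a percentage. This stands, and it limits the harm to the reported p-values. The documents nevertheless state hypotheses, name a test, set its level and promise its p-values, so that level should be the real one.

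Second, redaction is extensive. Apart from the blocks already mentioned, part of the sample size box in the Protocol Summary, the text after the success rule in SAP 4.3 and two SAP headings between 4.3 and 4.6 cannot be read. A one-eye or paired sensitivity analysis may sit there. That also stands, but it concerns a supportive analysis. The readable cells of Table 4-1 name the unadjusted test as the method for both primary endpoints.

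Third, rho is assumed, and at small values discreteness absorbs the effect. That is correct, and it is why the claim is only that 2.5% is not assured. The figures are also per test. The error of a claim that needs both tests to pass is bounded by the larger of the two sizes.

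Fourth, the effective-sample-size test is mildly conservative. At 50 eyes and rho 0.5 it needs 35 and 46 successes, where the exact paired distribution with known rho needs 34 and 45. This is fair. It is a reason to consider other cluster-valid methods, not to keep the unadjusted test as primary.

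**Conclusion.** The concern holds and should be fixed. The plan names a test that assumes independence, applies it to paired eyes, and states an error rate that this test does not guarantee. At the planned sizes of 50 to 60 eyes, true size per test is 2.7% to 7.4% for rho between 0.3 and 0.8, and 1.8% to 3.0% at rho 0.1. For Test 2 a rho of about 0.02 to 0.11 is enough to pass 2.5%, depending on the number of eyes.

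These figures rest on an assumed rho and on two evaluable eyes for every subject. They concern the p-values, not the percentages or the success rule as written.

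A lesser point of clarification concerns the stability criterion in SAP 2.1.2.1, "The 95% confidence interval for the mean rate of change in MRSE includes zero or a rate of change attributable to normal aging". The method for that interval is not stated in the readable text, so whether it allows for pairing is open.

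**What to change.** In Protocol 12.5.1 and SAP 4.2, 4.3 and Table 4-1, make the primary test subject-clustered before database lock. One concrete form:

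1. Estimate rho as 1 - (share of subjects with discordant eyes)/(2p(1 - p)), where p is the observed percentage. Truncate at 0, and set rho to 0 if p is 0 or 1.
2. Set n_eff = (eyes from subjects with two evaluable eyes)/(1 + rho) + (number of subjects with one evaluable eye).
3. Set x_eff = p x n_eff and take the p-value as I_p0(x_eff, n_eff - x_eff + 1). A non-integer n_eff then needs no rounding.
4. Keep the unadjusted exact test as supportive.

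Other cluster-valid choices, such as a subject-level exact or permutation test or one pre-specified eye per subject, would also answer the point. If redacted text already contains such an analysis, refer to it in Table 4-1. In Protocol 12.4 and SAP 2.1.2.1, state that the stability interval is computed with subject as the cluster.

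The work is wording and a few lines of code, with no extra patients, but the bar rises. At 50 eyes the Test 1 cut-off moves from 33 to 34, 35 and 36 at estimated rho 0.3, 0.5 and 0.8, and the Test 2 cut-off from 44 to 45, 46 and 46. Power with 25 subjects, for assumed true rates of 70% (Test 1) and 90% (Test 2):

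| rho | Unadjusted, T1/T2 | Clustered, T1/T2 |
|---|---|---|
| 0 | 78% / 77% | 75% / 72% |
| 0.3 | 75% / 75% | 64% / 61% |
| 0.5 | 74% / 74% | 58% / 53% |
| 0.8 | 72% / 73% | 51% / 38% |

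For rho of 0.3 and above, the unadjusted column is bought with an error rate over 2.5%, so not all of the difference is a true loss.

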### 12.2.1 Safety Analysis Set

The safety analysis set (SAF) will include all eyes for which refractive surgery is attempted with test device (regardless of success or failure). SAF will be the primary analysis set for the safety analyses.

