**Table 9–2** **Procedural Complications**

Treatment/Procedure Complication	Precaution(s) and Action(s) to be taken	Subject Status
Flap Creation incomplete or irregular	If flap creation is unsuccessful or irregular, THEN the flap should not be lifted and/or subject should not be treated	Subject should be followed as per Section 10.4.2.
Partial or incomplete LASIK ablation	IF LASIK ablation is not successfully completed, retreatment is not allowed.	Subject should be followed as per Section 10.4.2.

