## 10.4 Discontinued Subjects

### 10.4.1 Screen Failures

Subjects who were excluded from the study after signing the informed consent and prior to surgical procedures beginning (prior to eye drops for flap creation), are considered a screen failure. The Investigator must document the reason for screen failure in the subject's chart.

Subject numbers must not be re-used.

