### 10.4.2 Incomplete Treatments

If a subject's surgical treatment is started but discontinued due to complications or other reasons, every effort must be made to keep the subject in the study and to continue with the study required visits. For these subjects, appropriate follow-up assessments as per standard of care (including at minimum, AEs, slit lamp examination, UCDVA, manifest refraction, and BCDVA) should be conducted and collected. If the subject is not willing to complete all required follow-up visits, then document in the chart and exit the subject according to Section 10.4.3. See Section 11.6 for additional instructions for any adverse events.

*Note:* If drops are given for surgical treatment, but no laser procedure started and the surgery needs to be rescheduled, then reschedule surgery within the protocol defined visit window or follow rescreening instructions in Section 8.3.

*Note:* Please inform the Sponsor as soon as possible when an incomplete treatment occurs in order to discuss and confirm proper reporting and follow-up.

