### 10.4.3 Discontinuations

Discontinued subjects are individuals who voluntarily withdraw or are withdrawn from the study by the Investigator after the surgical procedure (eye drops given for flap creation), has begun.

Subjects may discontinue from study or study treatment at any time for any reason. Subjects may also be discontinued from study treatment at any time if, in the opinion of the Investigator, continued treatment poses a risk to their health.

For subjects discontinuing from the study after treatment, the Investigator must complete all Early Exit procedures according to Table 3-1, Schedule of Study Procedures and Assessments, if the subject is willing and able, and if in the opinion of the Investigator it is safe for the subject to do so.

The Investigator must document the reason for study or treatment discontinuation in the subject's chart.

To ensure the safety of all subjects who discontinue early, Investigators must assess each subject and, if necessary, advise them of any therapies and/or medical procedures that may be needed to maintain their health.

Subject numbers of discontinued subjects must not be re-used.

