### **Specific Events Relevant to this Protocol**

In addition to reporting all AEs (serious and non-serious) meeting the definitions, the Investigator must report any occurrence of the following as an ocular SAE:

- Diffuse lamellar keratitis (Grade 3 or above)
- Corneal infiltrate or ulcer

- Any persistent corneal epithelial defect at one month or later
- Corneal edema at 1 month or later (specify flap or bed)
- Epithelium in the interface with loss of 2 lines (10 letters) or more BCDVA
- Miscreated flap (lost, incomplete, too thin)
- Melting of the flap
- IOP with increase of > 10 mmHg above baseline on two consecutive examinations or an IOP greater than 30 mmHg on two consecutive examinations
- Haze beyond 6 months with loss of 2 lines or greater ( $\geq$  10 letters ETDRS) of BCDVA
- Decrease in BCDVA of greater than or equal to 2 lines ( $\geq$  10 letters ETDRS) not due to irregular astigmatism as shown by rigid contact lens refraction at 3 months or later
- Retinal detachment
- Retinal vascular accidents
- Ocular penetration
- Any other vision-threatening event

The Investigator must also report the following ocular AEs:

- Diffuse lamellar keratitis (Grade 2 or less)
- Corneal edema between one week and 1 month after the procedure
- Peripheral corneal epithelial defect at 1 month or later (location of the defect to be identified as on, off, or across the flap)
- Epithelium in the interface
- Foreign body sensation at 1 month or later
- Pain at 1 month or later
- Ghost/double images in the operative eye
- Flap is not of the size and shape as initially intended or resultant flap is misaligned

AEs that occur in association with a device that is used in conjunction with FS200 will be reported separately from those occurring with EX500.

This list is consistent with the categories provided in ANSI Z80.11 2012(R2017). Any other potentially sight-threatening event may also be considered serious based on the judgment of the Investigator and should be reported appropriately as delineated in Section 11.3.

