#### **12.7.1.2 Analysis Methods**

The SAF will be used for this analysis. The number and percentage of eyes experiencing each of the primary safety endpoints will also be calculated.

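### Does the safety analysis set leave out an eye whose flap fails before the excimer laser is used?

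*Protocol*

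**What the plan says.** Protocol Section 12.2.1 and SAP Section 2.2 define the SAF in the same words: "all eyes for which refractive surgery is attempted with test device (regardless of success or failure"). The Protocol summary (Section 3) and Section 12.7 repeat the definition. For the primary safety endpoint, Protocol Section 12.7.1.2 says "The SAF will be used for this analysis".

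The Protocol glossary names the EX500 as the only test product, and SAP Section 5.3 identifies the test device as the EX500. Section 10.2.11 puts FS200 flap creation before EX500 ablation. For a failed flap, Table 9–2 says "If flap creation is unsuccessful or irregular, THEN the flap should not be lifted and/or subject should not be treated", and refers the subject to Section 10.4.2.

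Three other places bear on when surgery starts:

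- Section 10.4.1: subjects excluded after consent but "prior to surgical procedures beginning (prior to eye drops for flap creation), are considered a screen failure".
- Section 10.4.2: "If drops are given for surgical treatment, but no laser procedure started and the surgery needs to be rescheduled", the operation is rebooked within the visit window or the subject is rescreened.
- Section 10.4.3: discontinued subjects are those who leave "after the surgical procedure (eye drops given for flap creation), has begun".

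Section 11.1 lists "Miscreated flap (lost, incomplete, too thin") among the events that must be reported as serious ocular adverse events. It also says that adverse events linked to devices used together with the FS200 "will be reported separately from those occurring with EX500".

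**The concern.** Three visible statements seem to combine badly. Entry to the SAF depends on the test device, the test device is the EX500 alone, and the flap is made first with another laser. If the flap fails and the eye is not ablated, an analyst who takes the definition literally could say that surgery with the test device was never attempted. The eye would then leave both numerator and denominator of the only primary safety endpoint, and it would leave because of a serious complication of the study procedure. A safety set should not select on outcome in that way, and two analysts could report different percentages from the same data.

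A second worry concerns the numerator. Protocol Section 11.3 classes the FS200 as a non-study marketed device whose adverse events are processed as spontaneous reports. That could be taken to mean that flap events do not count in the study percentage even for an eye that is in the SAF.

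**Working it through.** **Which reading the text supports**

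1. *Attempted against successful.* The SAF rests on an attempt, whatever its outcome. The full analysis set (Protocol Section 12.2.2) requires successful surgery. The two sets are built to differ on failed procedures, and a failed flap is one.
2. *Flap as part of the treatment.* The usage row of Table 9–1 describes flap creation as a required step before the laser portion of the treatment. Section 10.2.11 describes flap and ablation together as one operation, LASIK surgery.
3. *When surgery starts.* Sections 10.4.1 and 10.4.3 both place the start at the drops for flap creation. The note in Section 10.4.2 removes only the case where drops were given but no laser was started and surgery is rebooked.
4. *Status of a failed flap.* Table 9–2 sends it to Section 10.4.2, which covers treatment that was started and then stopped. That section keeps the subject in follow-up and asks the site to tell the sponsor promptly so that reporting can be agreed.
5. *Numerator.* The endpoint in Section 12.7.1 has no limit by device or cause, and the glossary counts an adverse event whether or not it is related to the investigational device. The Section 11.3 rule directs reports to the manufacturer; it does not define an analysis. The separate listing of events before test-device surgery (Section 12.7, SAP Section 5.3) is additional to the main summaries.

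An eye with a flap problem that is still ablated is in the SAF on either reading. Only eyes that never reach ablation are in question.

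**Size**

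The denominator is the planned 60 treated eyes (30 subjects; Protocol Sections 3 and 8). That figure is consistent with the plan's own rates: 25/(1 − 0.10) = 27.8, rounded up to 28, against 30 treated; 30/(1 − 0.10) = 33.3, rounded up to 34, against 35 enrolled. The documents give no expected ocular adverse event rate and no flap-failure rate, so there is no planned safety percentage to reproduce and the counts below are assumptions.

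Let N = 60 eyes start surgery, k stop at the flap, and x other eyes have an ocular adverse event.

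- Narrow set: x/(N − k)
- Wide set: (x + k)/N
- Difference: k(N − k − x)/[N(N − k)]

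| k | x | Narrow | Wide | Difference (points) |
|---|---|---|---|---|
| 1 | 0 | 0/59 = 0.00% | 1/60 = 1.67% | 1.67 |
| 1 | 6 | 6/59 = 10.17% | 7/60 = 11.67% | 1.50 |
| 1 | 12 | 12/59 = 20.34% | 13/60 = 21.67% | 1.33 |
| 2 | 0 | 0/58 = 0.00% | 2/60 = 3.33% | 3.33 |
| 2 | 6 | 6/58 = 10.34% | 8/60 = 13.33% | 2.99 |
| 2 | 12 | 12/58 = 20.69% | 14/60 = 23.33% | 2.64 |

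For scale, the exact 95% interval for 7/60 is 4.8% to 22.6%. This treats eyes as independent, which fellow eyes are not. A shift of 1.5 points is small beside it.

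The chance of at least one such eye is 1 − (1 − r)^60 for a per-eye rate r, again treating eyes as independent. Assumed rates of 0.2%, 1% and 3% give 11%, 45% and 84%. The documents do not favour any of these rates.

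**The case for a change.** The best case for a change is that the success-or-failure clause describes the outcome of an attempt with the test device and does not say when that attempt begins. Sections 10.4.1 to 10.4.3 set their boundary for screen failure, follow-up and discontinuation, and the SAF does not refer to them. SAP Section 5.3 names the EX500 in so many words. On the narrow reading the eye could also drop out of the percentages for problems during surgery (SAP Section 5.3.14), since Section 5.3 runs the safety analyses on the SAF. The data are already collected, so a clarifying sentence would cost little.

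Part of this stands. Neither document states the entry step, and the Manual of Procedures and the Deviations and Evaluability Plan, which might, are not available here. The rest is weaker. The EX500 wording in SAP Section 5.3 governs a listing of events before surgery, not membership of the set. Even on the narrow reading a flap event would fall into that listing, and Protocol Section 12.7 requires all adverse events from consent to exit to be accounted for, so the event would not disappear.

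The wider wording has drawbacks too. It would put eyes never exposed to the EX500 into the denominator of a percentage meant to describe the EX500, which is open to debate. It would also leave such eyes without ablation items, such as optical zone and residual stroma thickness, that SAP Section 3 summarises for the SAF.

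**Conclusion.** The concern does not call for a change. The entry step is an unstated detail. The protocol's account of when surgery starts, its handling of a failed flap and the contrast with the full analysis set all lead an analyst to count the eye. The numerator worry fails, because the endpoint is not limited by device and the Section 11.3 rule concerns where reports are sent.

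If the narrow reading were used, the primary safety percentage would fall by about 1.3 to 1.7 points for one such eye and 2.6 to 3.3 points for two. This assumes 60 eyes starting surgery and 0 to 12 other affected eyes. If no eye stops at the flap, the shift is zero. Protocol Section 12.7.1.1 and SAP Section 5.2 plan no safety test, and the endpoint has no target, so no conclusion of the study depends on which reading is used.
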